2. LAY SUMMARY

Treatment of sleep disturbances is mainly attempted through behavioral modifications or drug administration. However, behavioral approaches may fail, and certain drugs are associated with unwanted side effects or residual effects upon awakening (e.g. sleepiness, ataxia) which can increase the risks of falls and fractures. In addition, there can be systemic consequences of long-term medication use. An alternative method of manipulating sleep is by electrically stimulating the brain to directly influence the brain circuits underlying behavioural state. To date, there have been mixed results from stimulating superficial areas of the brain and, as far as we know, there has been no systematic attempt to influence deep brain activity using deep brain stimulation.

Many patients suffering from neurological diseases, such as Parkinson's Disease (PD), Multiple Systems Atrophy (MSA), Essential Tremor, Chronic Pain, and Epilepsy also have disrupted sleep. Currently, at stages where drug treatment do not offer adequate control of their primary neurological symptoms, these patients are implanted with a deep brain stimulation (DBS) system. This involves depth electrodes implanted into specific brain locations to deliver electrical stimulation to the targeted area..

The aim of this feasibility study is to investigate whether we can improve sleep quality in patients who have DBS devices implanted for existing neurological indications by delivering targeted stimulation patterns during specific stages of sleep using their existing DBS device. We will only use electrical stimulation frequencies that have been proven to be safe for patients. We will perform these studies in patients admitted to the hospital in order to examine the structure and quality of sleep as well as how alert patients are when they wake up, while also monitoring physiological markers such as brainwave activity, heart rate and blood pressure. Upon awakening, we will ask the patients to provide their subjective opinion of their sleep and complete some simple tests to see how alert they are compared to a night of no electrical stimulation.

We hope that our study will open new ways of optimizing sleep in patients with neurological disease who are implanted with DBS devices. We also believe that our findings will broaden the understanding of how the activity of deep brain areas influences sleep and alertness.

Interventions	Open and closed-loop electrical modulation triggered and based on ongoing sleep staging by researcher as well as automated closed-loop algorithm for stimulation.	Effect on autonomic measures such as heart-rate variability and blood pressure, as well as salivary cortisol levels	
 On awakening (post-baseline night and post-intervention) During day (post-baseline & intervention) Salivary cortisol levels measured on awakening each day (6am).
Comparator	Within-subject: their usual stimulation settings (stimulation at high/low frequency, as per established practice) Between-subject: different nuclei (stimulation sites)		

4.

4. ABBREVIATIONS

AASM	American Academy of Sleep Medicine
AMG	Amygdala
ANT	Anterior Nucleus of Thalamus
CL	Centro lateral Nucleus of Thalamus
CMT	Centro median Nucleus of Thalamus
CRF	Case Report Form
CTRG	Clinical Trials & Research Governance
DBS	Deep Brain Stimulation
DHRPO	Department of Defence Human Research Protection Official (U.S.)
DoD	Department of Defense (U.S.)
EMG	Electro-myogram
EOG	Electro-oculogram
GCP	Good Clinical Practice
GPi	Globus Pallidus Interna
HF	High-Frequency
HIP	Hippocampus
HRPO	Human Research Protection Officer
ICF	Informed Consent Form
IRB	Institutional Review Board
KSS	Karolinska Sleepiness Scale
LF	Low-Frequency
MSA	Multiple Systems Atrophy
MTLE	Medial Temporal Lobe Epilepsy
NREM	Non-Rapid Eye Movement Sleep
N1	Stage 1 of NREM
N2	Stage 2 of NREM
N3	Stage 3 of NREM
REM	Rapid Eye Movement Sleep
PAG/PVG	Periaqueductal Grey/Periventricular Grey matter
PD	Parkinson's Disease

PPN	Pedunculopontine nucleus
PI	Principal Investigator
SOP	Standard Operating Procedure
Stim	Stimulation
STN	Subthalamic Nucleus
USAMRDC	U.S. Army Medical Research and Development Command

5. BACKGROUND AND RATIONALE

Sleep disturbances such as insomnia, whose worldwide prevalence is approximately 35%, pose a heavy burden on communities by affecting quality of life through reduced sleep quality, disturbed diurnal functioning, as well as a bidirectional interaction with other diseases (reviewed in Morin et al 2015). Neurological disease in particular has a high association with sleep comorbidities. Movement disorders, apart from their well-known motor sequelae, are often accompanied by poor sleep quality and architecture. Notably, prevalence of sleep disturbances in Parkinson's Disease (PD) varies from 40 to 98% (Dhawan et al 2006), while both drug-naïve patients and those receiving treatment exhibit a decrease in delta oscillatory power compared to age-matched controls (Brunner et al 2002). Similarly, epilepsy has a bi-directional relationship with sleep (Bazil et al. 2017; Manni R, et al. 2010) and possibly a mechanistic role in epileptogenesis (Bower et al 2015 & 2017).

Currently, DBS is a treatment option for patients with movement disorders and epilepsy that show poor response to drug therapies. Patients are able to titrate the amplitude of stimulation under guidance, to help control disease symptoms. However, these stimulation parameters are constant (do not vary according to wake/sleep cycles or intrinsic brain activity), while the applied stimulation parameters are largely tailored based on disease symptom response only. Indeed, DBS targets a variety of regulatory networks with an involvement in sleep maintenance and regulation (including thalamo-cortical, basal ganglia, and connectivity to brain stem regions), the specific networks depending on disease state and mechanism of therapy (e.g. Sharma et al 2018). Thus, whether and how we can harness DBS for treatment of sleep disturbances is a question that remains largely unexplored.

In this study, we will investigate the feasibility of targeting DBS to modify sleep in patients with a range of brain areas implanted. The patients will have already been implanted with a DBS device for approved clinical indications, e.g. PD and epilepsy. We will aim to tailor the stimulation parameters according to available evidence (by changing the frequency and/or off periods according to sleep stage), in a way that optimizes sleep. More specifically, we wish to determine if amplitudes and frequencies of electrical stimulation that are clinically available to our patients might be beneficial for sleep induction and maintenance, or in fact disrupt sleep quality. Furthermore, we wish to minimize sleep inertia (the period of reduced alertness and performance capability upon awakening), ease sleep-wake transitions as well as control sleep depth. The population of the study will be patients with PD, other movement disorders, pain and epilepsy patients who have a DBS device already implanted.

We plan on recruiting patients with DBS leads in six primary targets of interest: STN, ANT, CMT, CL, HIP, AMYG. There are indications from previous findings (basic science/animal studies as well as some involving human participants) that these brain sites play roles in sleep modulation (summarized in table 1 below). These participants will be chronically implanted and thus not naïve to the effects of stimulation, but will have an established sleep pattern that has been influenced by their clinical programming. First, we will record baseline brain activity during sleep overnight and we will afterwards proceed to apply different stimulation patterns (low vs. high frequency) during different sleep stages. This will allow us both within-subject comparisons as well as greater efficacy and familiarity with individual sleep patterns.

There are no known risks of tailoring the stimulation frequency to sleep stage. Regarding the potential risks, the biggest risk would be provocation of an epileptic seizure by the electrical stimulation. This risk will be minimized by using previously established safe stimulation parameters determined by the clinicians caring for the patient. Other risks include possible disruption of sleep architecture and/or arousal during the first attempt to optimize the parameters. However, in this event, these settings would not be used further, and may help establish an algorithm for optimal sleep depth and appropriate arousal times. All frequencies and amplitudes that we plan to use in this study are already available on devices and clinical programmers, therefore ensuring patient safety. We will not use novel frequencies that have not been clinically tested. In participants with epilepsy we will avoid stimulation of epileptogenic foci to avoid seizure induction. In participants with chronic pain, we will test stimulation parameters while the patient is awake, to ensure good levels of pain relief and tolerability of the protocol.

With regards to the potential benefits, improving sleep depth and architecture through stimulation could lead to physical, psychological and cognitive benefits in our target clinical populations. The most immediately obvious benefits may be a reduction in sleep inertia, with better cognitive functioning after waking up from sleep. However, better sleep quality has also been associated with working memory improvements in older adults (Ellenbogen, 2005).

Target Area	Disease	Role in Sleep (if known)
AMG	Epilepsy	Consolidation of emotional memory. Possible relevance for PTSD (Van Der Helm et al. 2011)
ANT	Epilepsy	HF can disrupt sleep cycles (Voges et al. 2015)
CL	Epilepsy	Control of arousal. HF stimulation facilitates arousal from N3 (Redinbaugh et al 2020)
CMT	Epilepsy	CMT neurons can modulate brain-wide cortical activity during sleep and provides dual control of sleep-wake states (Gent et al. 2018)
Cortical	Epilepsy & Pain	Steriade (1997), McCormick & Bal (1997)
HIP	Epilepsy	Critical role in memory consolidation during slow-wave sleep
Other Potential Areas		
GPI	Dystonia & PD	HF Arousal from anesthesia (Moll et al. 2009)
HYP	Cluster HA	Control of sleep and arousal. (Saper et al. 2001)

Target Area	Disease	Role in Sleep (if known)
PAG/PVG	Pain	
PPN	PD & MSA	HF stimulation increased REM (Moro et al 2009)
STN	PD	HF stimulation improves sleep quality (Baumann-Vogel et al. 2017)

Table 1: Target brain areas of interest, neurological condition of participant group and roles in sleep modulation if known.

In addition to the patients with FDA approved DBS devices we will also analyze previously collected data from patients implanted with an investigational RC+S Summit device. The sleep and wake data from these patients was previously collected as part of an ongoing FDA-IDE G180224. The analysis of these previously collected data will focus on how low and high frequency stimulation impacts sleep electrophysiology. The analysis of the RC+S data will be included in the FDA-IDE G180224 yearly submissions.

6. OBJECTIVES AND OUTCOME MEASURES

Objectives	Outcome Measures	Timepoint(s) of outcome measure
Primary Objectives		
Feasibility of study	Ability to recruit planned participant number and carry out scheduled experiments in reproducible fashion	
 Analyses post-study completion Some evidence during interim analyses per group
Effect of stimulation on sleep stages	EEG changes (frequency changes, changes in EEG patterns and sleep structure)	
 During stimulation Post-stimulation at specific sleep stages

Secondary Objectives
 
Effect of stimulation on sleep inertia and vigilance & performance during the day
 
Controlling sleep depth and sleep-wake transitions
	
Performance on short and long test battery (see section 9.6.3)
 
Assessment of effect on latency to sleep onset and REM sleep, number of sleep cycles, duration of sleep stages, number of awakenings per night, sleep efficiency
	
 Upon awakening (post-baseline night and post-intervention) During the day (post-baseline and intervention) During intervention nights

Tertiary Objectives
 
Effect of stimulation on other measures of arousal
	
Effect on autonomic measures such as heart-rate variability and blood pressure, as well as salivary cortisol levels
	
 Overnight measurements Salivary cortisol levels measured upon awakening each day (6am).

7. STUDY DESIGN

This is a feasibility study that will take place in Mayo Clinic Rochester, MN. A parallel study will also be conducted at a UK site (Oxford University, UK) and University of California San Francisco (UCSF) under the same funding but this will be reviewed by their local IRB. Anonymized data will be shared between sites for analyses purposes.

Participants will be identified during their routine clinic visits and care and invited to participate in the study. Screening of interested potential participants will take into account pre-operative assessment data.

Testing will ensue (within a variable period from screening, but within the study timeline), over two visits to the epilepsy monitoring unit in Saint Marys Hospital (SMH), each consisting of two nights. Baseline sleep recordings will be obtained over the first night of the first visit, with the remaining nights consisting of stimulation trials. Questionnaires, daytime vigilance testing, autonomic parameters and cortisol levels will be collected as described in the sections to follow. No long-term follow-up is planned at this stage.

With regards to data collection processes, our population of patients have already been implanted with a DBS system (such as an FDA approved Medtronic Activa PC, Boston Scientific Vercise, Abbot Infinity systems). In addition, we will analyze data previously collected from patients with the RC+S Summit System under FDA-IDE G180224. The analysis of the RC+S data will be included in the FDA-IDE G180224 yearly submissions.

Note: A parallel study DBS devices currently under IDE investigations (such as Medtronic RC+S devices) will be pursued separately. Inclusion of patients with investigational devices under FDA investigational device exemptions will require prior approval from FDA.

We will leverage rules from the current AASM guidelines, technologies and methods for manual and automated sleep scoring using standard scalp polysomnography as well as novel methods we previously developed for sleep scoring using intracranial electrophysiology.

For perturbations, we will use the FDA approved clinician programmer and patient programmer. In this study, we specify as high frequency (HF) a stimulation range from 40 Hz to 250 Hz, while low frequency (LF) will be defined as 2 Hz to 40 Hz. All perturbations will be within the clinical range used and approved for DBS patients.

We will use a combination of subjective and objective measurements of sleep quality and efficiency to measure the impact of any sleep perturbations. The following objective metrics will be derived from visual/manual polysomnography (gold standard) & automated algorithm sleep staging:

1. Total sleep time.
2. Number of sleep cycles (switches of non-rapid eye movement (NREM) and rapid eye movement (REM) sleep).
3. Initial sleep and REM latencies (Time from beginning of study to the first stage of sleep, and from beginning of sleep to first REM sleep onset).
4. Duration of N1, N2, N3, and REM stages, and the duration of NREM (sum of N1,N2,N3)stages.
5. Sleep efficiency (100*total sleep time/time in bed).
6. Number of awakenings during night, including arousals per hour and duration of time spent awake after initial sleep onset (i.e., wake after sleep onset time)
7. Apnea-hypopnea and respiratory disturbance indices (the frequency of stop or reduced breathing episodes, and respiratory arousals per hour)
8. Periodic limb movement indices (the frequency of periodic leg movements of sleep per hour)
9. Measures of arousal during sleep
 - a. behavioural macrostate observations such as eye opening or blinking that can be assessed in video recordings

- b. microarousal observations defined exclusively by cortical fast frequency shifts (ie, >14 Hz rhythms) lasting 3 seconds or longer, with or without added autonomic measures of tachycardia.
 - c. Spectral composition of the sleep stage specific EEG over the 0.25-32 Hz frequency range
 - d.
10. Salivary samples to characterize awakening levels of cortisol will be obtained in the morning (~6AM) at the end of each night.
- 11.
12. Questionnaires will be administered to patients as per the list below:
 - Upon enrollment/prior to their visit:
 - The following questionnaires or tasks will be administered to or completed by both the Epilepsy and Parkinson's disease Cohort at specified time points (see schedule of events)
1. Neurological Exam & Mini-Mental State Examination (MMSE).
2. Current medications and medication history. Medications will be kept stable
3. Mood assessment with Beck Inventory for Anxiety and Depression
4. Quality of life evaluation (QOLIE-31) questionnaire.
5. Patient sleep diary (bedtime, awakening time, arousals/sleep disturbances, perceived sleep quality).
6. Karolinska Sleepiness Scale (KSS) (Akerstedt and Gillberg, 1990).
7. Profile of Mood States Scale (POMS) (McNair, Lorr and Doppleman, 1971)
8. Psychomotor Vigilance Task (PVT) (as in Santhi et al. 2013)
9. Karolinska Drowsiness Test (KDT) (Akerstedt and Gillbert, 1990)

These questionnaires are specific to the Epilepsy Cohort only:

10. Liverpool Seizure Severity Scale and Seizure Severity Questionnaire (LSSS).
11. Seizure Severity Questionnaire (SSS).
12. Mayo Epilepsy Short Assessment.
13. These questionnaires are specific to the Parkinson's disease Cohort only: Movement Disorder Society Parkinson's Disease Rating Scale (MDS-UPDRS) (Goetz et al 2008).

14. Parkinson's Disease Sleep Scale (PDSS) (Trenkwalder et al. 2011). This will be completed by the Parkinson's Disease Cohort only. Tasks and questionnaires are described in more detail in section 9.6.3.

8. PARTICIPANT IDENTIFICATION

8.1. Study Participants

Patients suitable for this study will be identified by either the clinical and research teams. Suitable candidates will be reviewed with the clinicians responsible for the clinical care of the patients. The participants will be allowed to exit the study at any point without any changes to their routine medical care. The initial assessment will be carried out by the research team working with the patient's primary neurologist.

8.2. Inclusion Criteria

- DBS in one of the defined nuclei of interest during the period of the study
- Male or female, aged 18 years and above
- Be willing and able to give written and oral informed consent
- Ability to complete all required study procedures including travelling to Mayo Clinic and staying overnight
- All women of childbearing potential and women who have been amenorrheic for less than 1 year must practice effective contraception during the study. This includes a barrier method such as condom or diaphragm with spermicide; barrier intrauterine device (IUD) or abstinence.

8.3. Exclusion Criteria

The participant may not enter the study if ANY of the following apply:

- Cognitive impairment (judged by the clinician taking consent as not having sufficient mental capacity to understand the study and its requirements). This is including anyone who, in the opinion of the clinician taking consent is unlikely to retain sufficient mental capacity for the duration of their involvement in the study.
- Patients with any other medical condition that would interfere with study conduct or make it unsafe for them to participate

9. PROTOCOL PROCEDURES

9.1. Recruitment

Potential participants will be identified by the clinical and research team as suitable candidates. Recruitment will take place in outpatient or pre-operative assessment clinic, as well as during assessment for suitability for DBS surgery. They will first be approached by the clinical team and if they indicate that they are interested in taking part, will then be approached by a researcher.

9.2. Visit-1 Screening and Eligibility Assessment

Screening and eligibility will be assessed during the patients' clinic visit schedule or with a telephone interview. They will therefore have already had a detailed medical and drug history as per inclusion/exclusion criteria to this study, and this information will be available to their clinician

(recruiting for the study). If a potential participant is interested and agrees to further screening (to exclude medical conditions making participation unsafe, as per listed exclusion criteria), this will be documented in the patient's notes (relevant to the clinic visit) by the recruiting clinician.

The patient will be provided with all relevant study information and resources (such as the consent form and patient information sheet). They will be offered the choice of being screened after a future scheduled clinic visit, or at a separate visit solely for study purposes. This will ensure optimal comfort and minimal travel time.

Prior to any screening assessments we will obtain written consent. Upon screening, they will be asked for any changes/updates on their medication schedule or if any other conditions have developed. In addition, physical examination (at point of entry, in addition to the prior one as per pre-operative protocol) will ensure participant fitness for participation.

There will be no exceptions made regarding eligibility, i.e. each participant must satisfy all the approved inclusion and exclusion criteria of the protocol. Changes to the approved inclusion and exclusion may be made by substantial amendment only. We do not anticipate rescreening excluded potential participants.

9.3. Informed Consent

The participant must personally sign and date the latest approved version of the Informed Consent form before any study specific procedures are performed.

Written and verbal versions of the Participant Information and Informed Consent will be presented to the participants detailing no less than: the exact nature of the study; what it will involve for the participant; the implications and constraints of the protocol; the known side effects and any risks involved in taking part. It will be clearly stated that the participant is free to withdraw from the study at any time for any reason without prejudice to future care, without affecting their legal rights, and with no obligation to give the reason for withdrawal.

The participant will be allowed as much time as wished to consider the information (at least 24 hrs.), and the opportunity to question the PI, research team, or other independent parties to decide whether they will participate in the study. Written Informed Consent will then be obtained by means of participant dated signature and dated signature of the person who presented and obtained the Informed Consent. The person who obtained the consent must be suitably qualified and experienced and have been authorized to do so by the Principal Investigator. A copy of the signed Informed Consent will be given to the participant. The original signed form will be retained at the study site.

9.4. Enrollment

Patients enrolling in the study will be recorded in an encrypted study database on a password-protected Mayo Clinic computer. The team will identify patients who have been previously implanted with a DBS device and a contact call will be scheduled after liaison between the clinical team. During this, visit times and traveling arrangements will be discussed.

9.5. Blinding and code-breaking

There will be no blinding in the study and therefore no code-breaking procedure is required.

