9.6. Description of study intervention(s), comparators and study procedures (clinical)

9.6.1. Description of study intervention(s)

We will use both an open and a closed-loop approach to investigate sleep perturbations through stimulation deep brain targets. As previously mentioned, FDA approved clinician or patient programmers specific to the implanted device will be used at the open-loop stage, to explore the effect of available stimulation patterns when they are synchronized with different sleep stages. A physician/sleep technician team will be overseeing the delivery of stimuli during real-time sleep scoring on testing nights. See Appendix A. for example stimulation paradigms

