Upon awakening (at a time decided based on the sleep diary), a salivary sample will be obtained for morning cortisol. Participants will complete specific tasks at the time of awaking, and again at 30 minutes and 60 minutes post awaking.. These tasks will consist of the KSS, Mood, KDT, , , and PVT.

During the intervening day, the patients will be allowed to read, watch television, and socialize with caregivers, as well as complete tasks and questionnaires.

Testing/stimulation night:

We will use the programmers in an initial open-loop approach during the first visit, to see if a pattern can help optimize sleep stages and perturb sleep patterns. We will reconfigure each subject with polysomnography system and ensure it is still operating per requirements. The intent is to provide a consistent environment over both nights. We will again capture EEG (and if available, intracranial data). We will use real-time classification of sleep architecture to perturb the networks with variants of stimulation (see tables per target in Appendix A). For the initial sleep cycles, we will be using manual (open loop) interventions by the sleep monitor and the site clinician and scientist. In parallel, the laptop algorithm will be running a prototype closed-loop control to demonstrate the bridge to automated closed loop control. The output of the algorithm and stimulation commands will be logged and compared to the manual interventions.

Upon waking, a salivary sample will be obtained for measuring of early morning cortisol. The cognitive tasks will be performed as listed previously, to assess sleep inertia and other response variables. Subjective questionnaires will be administered post-cognitive screen. Cognitive tests will continue throughout the day to assess variation in the patient's performance.

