22. APPENDIX A

Stimulation and Medication parameters

Sites: Amygdala (AMG), Hippocampus (HIP), Anterior Nucleus Thalamus (ANT), Centromedian Thalamus (CMT), Central Lateral Thalamus (CL), Cortex, Subthalamic Nucleus (STN), Globus Pallidus Interna (GPI)

Stimulation: Standard (clinical DBS), Low frequency (2 - 30 Hz), High frequency (40 - 200 Hz). The stimulation parameters will be tested with physician at the bedside to ensure that stimulation does not produce side effects or symptoms.

Example of Experimental Stimulation Paradigm

Night 1	Wake	Light Out/Wake	N1	N2	N3	REM	N1	N2	Rem	Awake	Testing
Stim State	Standard	Standard	Standard	Standard	Standard	Standard	Standard	Standard	Standard	Standard	Standard
Medication	Standard	Standard	Standard	Standard	Standard	Standard	Standard	Standard	Standard	Hold until testing completed	
Night 2											
Stim State	Standard	Standard	off	off	low	off	off	low	off	Standard	Standard
Medication	Standard	Standard	Standard	Standard	Standard	Standard	Standard	Standard	Standard	Hold until testing completed	

Night 1	Wake	Light Out/Wake	N1	N2	N3	REM	N1	N2	Rem	Awake	Testing
Stim State	Standard	Standard	Standard	Standard	Standard	Standard	Standard	Standard	Standard	Standard	Standard
Medication	Standard	Standard	Standard	Standard	Standard	Standard	Standard	Standard	Standard	Hold until testing completed	
Night 2											
Stim State	Standard	Standard	off	off	off	high	off	off	high	Standard	Standard
Medication	Standard	Standard	Standard	Standard	Standard	Standard	Standard	Standard	Standard	Hold until testing completed	

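### With no blinding at all, the self-rated and effort-dependent secondary outcomes are open to expectation bias; at the second visit a randomised, undisclosed night order would reduce it

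*Combined protocol and SAP*

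**What the plan says.** Section 9.5 is a single sentence: "There will be no blinding in the study and therefore no code-breaking procedure is required".

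Section 6 lists as a secondary objective "Effect of stimulation on sleep inertia and vigilance & performance during the day", measured by the test batteries. Section 9.7 sets the tasks at waking, 30 minutes and 60 minutes: "These tasks will consist of the KSS, Mood, KDT, , , and PVT". After the stimulation night, "Subjective questionnaires will be administered post-cognitive screen"; section 9.8 repeats this for the second visit. KSS, mood and the questionnaires are self-ratings, and the PVT depends on effort. The KDT is a resting EEG (section 9.6.3).

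The second primary objective in section 6, beside feasibility, is measured by "EEG changes (frequency changes, changes in EEG patterns and sleep structure".

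On delivery, section 9.6.1 uses the programmers "to explore the effect of available stimulation patterns when they are synchronized with different sleep stages". The first example in Appendix A gives the second night's device states, from wake to morning testing, as "Standard Standard off off low off off low off Standard Standard".

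On order, section 7 makes the first night of the first visit the baseline, and section 9.7 uses its data to build the later patterns. Section 9.8 describes an adaptive night and a control night (open loop or off). It does not state their order and describes no randomisation.

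**The concern.** A participant who believes that last night was the one meant to improve sleep may report less sleepiness, better mood or better sleep, and may try harder on the PVT. That would produce a difference between nights on a secondary outcome with no effect of stimulation behind it. The comparison is within the person, so each participant can set one night against another in the light of what they know.

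This matters because section 11.2 plans to relate stimulation to the cognitive measures and questionnaires, and section 5 names reduced sleep inertia among the most immediate possible benefits. An improvement in these ratings could not be separated from the participant's knowledge of the condition.

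**Working it through.** **The plan's own figure.** Section 11.3 takes at least 3 patients in each of 5 electrode locations: 3 × 5 = 15, which reproduces. It says effect sizes are unknown, and section 11.7 gives no numerical significance level, so there is no power calculation to rework.

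**Can the night be concealed?**

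| Visit | Order | Can the participant be kept unaware? |
|---|---|---|
| First (9.7) | Baseline, then stimulation; fixed because the second night is built from the first | No. The sequence is fixed and knowable, and section 9.3 requires consent to explain what the study involves |
| Second (9.8) | Adaptive and control nights, order not stated; both draw on first-visit data | Yes, in part. Neither night is described as depending on the other, and no procedure needs the participant to know which is which |

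Concealment at the second visit means something only if the order varies between participants. If everyone followed one order, it would be nominal.

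**Size, as an illustration.** Assumptions that are not in the plan: no true effect; knowledge of the condition shifts the mean paired difference by b standard deviations of that difference; one pooled two-sided 5% paired t-test. The chance of a significant result comes from the noncentral t distribution with n − 1 degrees of freedom and noncentrality b × √n.

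For n = 15, √15 = 3.873:

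| b (assumed) | b × √15 | False-positive rate |
|---|---|---|
| 0 | 0 | 5.0% |
| 0.2 | 0.775 | 11.2% |
| 0.3 | 1.162 | 19.2% |
| 0.5 | 1.936 | 43.8% |

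For n = 3 in one target and b = 0.5, the noncentrality is 0.5 × 1.732 = 0.866 and the rate is 8.4%.

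**Effect of partial masking.** Suppose a proportion p guess the night correctly, and a wrong guess shifts the rating equally the other way. The mean shift becomes b × (2p − 1); the SD is held fixed. For b = 0.5 and n = 15:

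- p = 0.5: shift 0, rate 5.0%
- p = 0.7: 0.5 × 0.4 = 0.2, rate 11.2%
- p = 0.9: 0.5 × 0.8 = 0.4, rate 30.3%
- p = 1: shift 0.5, rate 43.8%

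Even imperfect concealment lowers the rate under these assumptions.

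**The case against.** **The reach is narrow, and the study is openly exploratory.** This stands. The primary outcomes are feasibility and EEG or sleep structure. The other secondary objective (latencies, stage durations, awakenings, efficiency) comes from polysomnography, and the KDT is EEG. Participant expectation bears directly on only part of one secondary objective. The exploratory label does not remove the point, since sections 11.2 and 11.7 still plan significance testing.

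**Masking may not hold.** This stands in part. A reader might infer from Appendix A that usual settings are always back at waking, so participants could not tell the nights apart. The appendix gives examples only. Sections 9.7 and 9.8 allow off conditions, section 9.10 says symptoms may return when the device is off or reduced, and section 5 has chronic pain participants try the parameters while awake. Staff who know the order may also give cues.

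**The size is assumed.** This stands. Nothing in the documents supports a particular shift, and no section specifies a pooled paired t-test. Section 11.2 leaves the methods open and falls back on consistency and trends where testing is not possible.

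**The sleep diary is weak evidence.** This stands. The item "Patient sleep diary (bedtime, awakening time, arousals/sleep disturbances, perceived sleep quality" appears in section 7 under a heading about enrolment and the time before the visit, and its only described uses are to set bedtime and waking time. The text of the schedule in Appendix B is not available to show whether it is repeated after study nights. The point rests on KSS, mood, the PVT and the post-night questionnaires instead.

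**Conclusion.** The concern holds in a limited form. Section 9.5 excludes all blinding without a reason, and the self-rated and effort-dependent secondary outcomes are therefore open to expectation bias of unknown size. At the second visit the plan could reduce it cheaply. The change is worth making, but the primary outcomes do not hinge on it.

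Three stronger readings are not supported:

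- **That these outcomes are shown to be biased, or that 44% is this trial's error rate.** No section says participants are told which night is expected to be better. The 11% to 44% range depends on the assumed shifts and on a pooled test of 15 patients; in a single target of 3, a 0.5 SD shift gives 8.4%.
- **That every night could be masked at almost no cost.** The first visit's order is fixed for a scientific reason and can be known. Masking cannot repair the contrast of baseline with stimulation.
- **That participant expectation undermines the primary result.** The EEG and sleep-structure outcome is not self-rated.

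**What to change.** Revise section 9.5, with matching text in sections 9.3 and 9.8:

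1. Randomise the order of the adaptive and control nights at the second visit.
2. Tell participants at consent that this order will not be disclosed until the last morning's tests are done.
3. After each morning's tests at that visit, record the participant's guess of the condition, and report the guesses beside the self-rated and PVT results.
4. Keep overnight and bedside clinical staff unmasked, so that supervision is unchanged.
5. State that first-visit comparisons of baseline with stimulation on self-ratings are descriptive, because the order is fixed and known.
6. State that masking is partial where a change in settings is felt.

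The cost is some consent and protocol wording, a randomised order for two nights, and one extra question each morning. The sample size does not change. The main drawback is incomplete masking, which the recorded guesses would help to show.
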